A Study About the Impact of Intensive Instruction on the Use of
Aricept and the Reasons for Discontinuation in Patients With
Alzheimer's Disease

Clinical study protocol

Protocol# ART-2013-01
(NCT01972204)

List / abbreviations and definitions of abbreviations and terms

Acronym	Expression not to be omitted (definition)
AChE	Acetylcholine esterase : acetylcholinesterase
AD	Alzheimer's disease : Alzheimer's dementia
ADL	A ctivities of D aily L iving : daily living behavior
AE	Adverse event : adverse event
BPSD	Behavioral and Psychological Symptoms of Dementia : behavioral and psychological symptoms of dementia
CRC	C linical research coordinator: test coordinator over ter
DSM	Diagnostic and Statistical Manual of Mental Disorders : Diagnostic Statistics Manual of the American Psychiatric Association
FAST	Functional Assessment Staging : Dementia severity rating scale
MMSE - J	Mini-Mental State Examination - English : Mental State Short Time Test - Japan Version
NMDA	N-methyl-D-aspartate : N methyl D aspartic acid
SAE	Serious adverse event : serious adverse event

summary

item	Contents
Study name	A Study About the Impact of Intensive Instruction on the Use of Aricept and the Reasons for Discontinuation in Patients With Alzheimer's Disease
The purpose	The purpose of this study is to examine the influence of the instruction on the use of Aricept with educational brochure on the 48-week medication persistence and to assess the reasons for discontinuation.
Examination design	Multicenter joint randomized parallel group comparison study comparative study
Target patient	
Alzheimer type dementia patients
 
Selection criteria
 
 1) Patients meeting DSM- IV diagnostic criteria for Alzheimer's dementia 2) Patients who agreed with this research (consent from patients should be acquired as much as possible and consent from substitute is essential) 3) We agree to cooperate with this research, provide necessary patient information, patients with families or carers who can accompany at the regular visit date 4) Outpatient from home 
Exclusion criteria
 
 1) Patients receiving treatment for AChE inhibitors (donepezil, galantamine, rivastigmine) , and NMDA receptor antagonists (memantine) within 4 weeks before consent acquisition 2) Patients with dyspepsil hydrochloride preparations or hypersensitivity to piperidine derivatives 3) Patients are also other test drug which has received the administration of investigational drugs within 12 weeks before the start of administration of study drug 4) Other patients whose clinical research doctor deemed inappropriate as subjects
Target case number	150 cases
Drugs used	
Aricept ® products (commercially available)
 
 · Tablets 3 mg , tablets 5 mg , tablets 10 mg Fine grain 0.5 % · D tablets 3 mg , D tablets 5 mg , D tablets 10 mg · Oral jelly 3 mg , Oral jelly 5 mg , Oral jelly 10 mg · Dry syrup 1% 
Normally, once 3 mg 1 day as donepezil hydrochloride in adults Starting from 1 to 2 weeks 5 mg And orally administered. For advanced Alzheimer's type dementia patients, 5 mg In 4 weeks

	
or more, 10 mg . Further, it should be reduced according to symptoms.
 
Fine: Normal, for adults once a day 0.6 g Starting from 1 to 2 weeks 1.0 g And orally administered. For advanced Alzheimer type dementia patients, 1.0 g In after more than 4 weeks, 2.0 g . Further, it should be reduced according to symptoms.
 
Dry syrup: usually, once a day for adults 0.3 g It starts from 0 after one to two weeks. 5 g And orally administered. The high degree of Alzheimer-type dementia, 0.5 g In 4 weeks or more, 1.0 g . Further, it should be reduced according to symptoms.

Test method	
Clinical research personnel to query the allocation group to promptly clinical research secretariat after consent from the subject has been acquired ("informed consent file" in due strengthening leadership group / Normal leadership group), the administration of Aricept ® Start. Among the study period of between 48 weeks, the subjects required date to visit (2 weeks, 12 weeks, 24 weeks, 48 weeks, increase the time from the donepezil hydrochloride 5 mg to 10 mg), examination of the provisions · Perform observation (compliance with medication, cognitive function test, adverse events , concomitant medication).
 
Enhanced leadership group due to "informed consent file", intends line medication guidance using the "informed consent file" to the required date to subject himself and family or caregiver.
 
If you stop taking Aricept ® medication, investigate until the reason is clear .

Evaluation items	
Key evaluation items
 
 - Aricept ® medication continuation rate when medication after 48 weeks - Aricept ® medication discontinuation at the time of reason 
Secondary endpoint
 
 - Aricept ® factor analysis of the impact on the medication continued
analysis	
Aricept ® medication continuation rate of 48 weeks compared with strengthening leadership group and the normal guidance group due to "informed consent file". Aggregates the reason at the time of Aricept ® medication discontinuation, to compare the reason for terminating between groups. In addition, the factors that affect the Aricept ® medication continuously analyzed by logistic regression analysis.

Medical institutions	15 facilities
Research period	After the Joint Ethics Committee approval to 2017 Dec.

table of contents

1. [Background · Preface](#)
2. [Purpose of clinical research](#)
3. [Object](#)
 - 3.1. [Selection criteria](#)
 - 3.2. [Exclusion criteria](#)
 - 3.3. [Definition of cancellation example](#)
 - 3.4. [Additional Supplementary Items in Canceled Example](#)
- Four. [Explain to the subject and obtain consent](#)
- Five. [Clinical research method](#)
 - 5.1. [Clinical research design](#)
 - 5.2. [Test outline](#)
 - 5.3. [Study participation schedule period of subjects](#)
 - 5.4. [Drug information](#)
 - 5.5. [Dose / administration method and administration period / method of use](#)
 - 5.6. [Assignment method](#)

Alzheimer type dementia (AD) is a progressive neurodegenerative disorder, with a decline in cognitive and memory ability, progressive disorder in daily living behavior, various symptoms of mental symptoms and behavior disorder¹⁾. Along with the rapid aging, the prevalence of dementia in Japan is increasing, according to the announcement of the Ministry of Health, Labor and Welfare study group in May 2013 (Representative Takashi Asada Tsukuba University), 65 years of age or older The prevalence of dementia among elderly people is estimated at 15%, which is said to be 4.62 million at 2012. AD is pathologically characterized by generalized cerebral atrophy and senile plaques of the cerebral cortex and neurofibrillary tangles. In addition, neurochemical studies have reported reduction of acetylcholine (ACh) mainly in forebrain and decreased activity of choline acetyltransferase which is ACh synthase, and the functional deterioration itself in intracerebral cholinergic nerve itself is the most essential "Choline hypothesis" to be said to be a pathological condition began to be cast.

Aricept® (generic name: donepezil hydrochloride) is an acetylcholinesterase (AChE) inhibitor created by Eisai Co., Ltd. It is an AD therapeutic agent having an action of increasing ACh concentration in the brain. In Japan, in October 1999 tablets (3 mg, 5 mg) were approved for the suppression of the progress of cognitive symptoms in mild and moderate AD, and in tablets (3 mg, 5 mg) as approval, in August 2007 irrespective of severity, Suppression of progress of cognitive symptoms in all AD was recognized as efficacy and effect. With respect to the dosage form additional, fine granules in March 2001, orally disintegrating in February 2004 (D) Tablets (3 mg, 5 mg), with the change of dosage regimen in August 2007, tablets (10 mg), D tablet (10 mg), oral jelly (3 mg, 5 mg, 10 mg) in July 2009, and dry syrup in February 2013.

Aricept® once, suspended (6 weeks or 4-8 weeks) Then, the case of no treatment cognitive function that is equivalent reported²⁾, compliance continuation rate of Aricept® under the actual clinical, low values (Table - 1). According to the report³⁾ of Watanabe et al., When carried out understanding of drug therapy with pathology and Aricept® of AD, medication instruction classroom with the aim to improve the medication adherence of the (Aricept classroom⁴⁾ to the patient and family, medication continuation rate although the improvement of is Ru recognized, yet, a patient of about 30% in one year has led to discontinuation. In addition, the reason that lead to medication discontinuation of Aricept®, the details are to grasp the unknown is often a (eg. Visits and the like that are no longer), the reason for terminating also in order to address the measures for medication continuation rate improved details There is a need.

Table - 1 medication continuation rate of Aricept ® under real clinical

	Specific usage record survey A ⁵⁾	Specific usage record survey B ⁶⁾			Watanabe 's report ³⁾
Object	Mild	Height			Mainly mild, moderate
Example number	640 cases	824 cases			About 50 cases
period	3 months	6 months	1 year	2 years	1 year
Drug continuation rate	59.7 %	83.7 %	68.9 %	50.9 %	49.2 %
Aricept Classroom Drug continuation rate at the time of implementation					73.1 %

Eisai Co., Ltd., has been created with the patient and family that medication Aricept ® a description for the tool for caregivers "informed consent file". This tool explains the pathology of AD , the significance of medication by Aricept ® , side effects, etc. , and aims to improve the continuation rate of Aricept ® medication by deepening the understanding of patients and their families and carers .

In the present study, strengthening of medication instruction using the tool to verify the impact on the Aricept ® medication continuation rate. In addition, in subjects medication of Aricept ® has reached the stop, investigate the reason for discontinuation in more detail, you analyze the background factor.

As a result of this study, we hope to build a standard dosing guidance method for drug treatment of Alzheimer type dementia and accumulate useful information for measures to improve the medication continuity rate .

2. Purpose of clinical research

The purpose of this study is to examine the influence of the instruction on the use of Aricept with educational brochure on the 48-week medication persistence and to assess the reasons for discontinuation. To examine the influence of the instruction on the use of Aricept with educational brochure comparing to the ordinary instruction on the 48-week medication persistence and to assess the reasons for discontinuation.

3. Object

Alzheimer disease patients

3.1. Selection criteria

Target patients who meet all of the following criteria

- 1) Patients conforming to the diagnostic criteria for Alzheimer type dementia by DSM - IV
- 2) Patients who agreed with this research (consent from patients should be acquired as much as possible and consent from substitute is essential)
- 3) We agreed to cooperate with this research, provide subject information necessary for this research, patients with families or caregivers who can accompany at the regular visit date
- Four) Outpatient from home

3.2. Exclusion criteria

Patients who conflict with any of the following will not be included in this clinical study

- 1) Patients AChE inhibitor within 4 weeks prior informed consent (donepezil, galantamine, rivastigmine), and are receiving medical NMDA receptor antagonists (memantine)
- 2) Patients with dyspepsil hydrochloride preparations or hypersensitivity to piperidine derivatives
- 3) Patients are also other test drug which has received the administration of investigational drugs within 12 weeks before the start of administration of study drug
- Four) Other patients whose clinical research doctor deemed inappropriate as subjects

[Rationale for setting]

1) Because there is concern about the influence on the evaluation of drug continuation rate , 2) to 3) for safety consideration

4) In order to leave room for clinical research doctors to consider whether to participate in this clinical study considering the safety of the subject taking the general factors other than those mentioned above into consideration

3.3. Definition of cancellation example

During the clinical study period , Medication of Aricept ® If you need to abort occurs, if it is found that to stop the medication of Aricept ®, or when it becomes the patient was transferred, non-visit by the institutionalization and hospitalization, etc., the case became untraceable It is handled as a discontinued example. In addition, even if you change the Aricept ® to generic drugs handled as a discontinued example.

In addition, we are dealing with a subject that is not called off example with a "medication continue".

The doctor in charge of clinical research investigates the reasons for suspension (classification ① and classification ② below) until the reason becomes clear in the discontinued example and records it in the case report.

[Reason classification of ①] (1 only one selection)

- 1) Doctor's judgment
- 2) Hope and judgment of the subject himself / herself
- 3) Hope , judgment of family member or carer

[Reason classification of ②] (select one or more)

- 1) Adverse event
- 2) Insufficient effect
 - (A) Effect on cognitive function
 - (B) Effect on ADL
 - (C) Effect on psychological symptoms
 - (D) Other: Free description
- 3) Change to other oral preparations (galantamine, memantine) (1 2) Reason for change other than 12) : Free description)
- Four) Change to patch agent (rivastigmine) (1 2) Reason for change other than 12) : Free description)
- Five) Change to generic drug

- 6) Aricept ® drug discontinuation due to hospital entry, ward hospitalization (entry to nursing home health care facility, hospitalization of comprehensive medical system etc)
- 7) Withdrawal of treatment due to visiting difficulties (eg family members or carers were absent)
- 8) Discontinuation of therapy due to medication assistance burden increase
- 9) Refusal (if the subject refuses to take the test medicine and the reason is unclear)
- 10) Transfer , facility entry , inpatient due to hospitalization
- 11) Others: it corresponds to the freedom described (12 if the reason is unclear))
- 12) Unknown (When it becomes impossible pursuit, reason is unclear etc.)

3.4. Additional Supplementary Items in Canceled Example

Investigate the date of discontinuation and state it in the case report.

Even after discontinuation, when continuing medication for Aricept ® (for example, in case of inability to visit by transfer, facility entry , hospitalization, etc) , follow up will take place at the prescribed visit points (2 weeks, 12 weeks, 24 weeks, 48 weeks) At the time of the period, investigate the medication situation of Aricept ® by phone etc. and describe it in the case report.

If there is use of Alzheimer's type dementia treatment drug (including generic drugs) after discontinuation, as follow up, investigate the medication situation of the therapeutic medicine on the telephone etc. at 48 weeks and describe the contents in the case report .

4. Explain to the subject and obtain consent

This doctor in charge of clinical research will fully explain the content of this clinical study etc. to subjects and substitutes . Give subjects and substitutes enough time to ask questions and whether to participate in this clinical study or not before confirming that we have understood the content of this clinical study well and before starting Obtain written consent from the principal (as far as possible) and from the substitute for free participation in participation in this clinical study .

The consent document, describes the clinical research physician and agreed subjects (as possible) was carried out, Daidaku's signed or serial name seal, dating. In addition, if the CRC · pharmacist etc complementarily explained, the cooperating person also signs,

signs, signs, and writes dates. One copy of the original shall be kept in the chart and the copy shall be given to the subject.

During this clinical study period, it can affect the willingness of subjects and Daidaku's about whether you want to join to continue to subject and Daidaku's new important information may be related to the consent of, or this clinical study, If sexual information is obtained, the clinical research representative promptly revises the consent explanation document based on the information and obtain approval from the joint ethics committee. Clinical research representatives will provide clinical research physicians with a revised consent statement . The doctor in charge of clinical research should promptly explain the information to the subject and the substitute, obtain the reconsideration by free will about the continuing participation in this clinical study, copy the copy of the consent form and the revised explanatory document to the subject .

[figure not shown]
In addition, subjects and substitutes can withdraw their consent at any time even after agreeing to participate in this clinical study, and shall not suffer any disadvantage due to withdrawal of consent .

5. Clinical research method

5.1. Clinical study design

Multicenter joint randomized parallel group comparative study

5.2. Test outline

1) Taking medication by "Informed consent file" (Attachment 2)

In strengthening leadership group due to "informed consent file", during the visit of the provisions (the second week [at the time increased from donepezil hydrochloride 3 mg to 5 mg], 12 weeks, 24 weeks, 48 weeks, and the increase at the time) from the donepezil hydrochloride 5 mg to 10 mg, use the "informed consent

file", the pathology of AD, the significance of drug therapy with Aricept®, side effects, etc. to the subject himself and family or caregiver explain.

2) Confirmation of reason for canceling medication

If medication is stopped, confirm the reason. If you did not visit the clinical research physician, CRC pharmacist or the like to perform the investigation until the clear reason by telephone or the like.

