7.1. Observation and inspection schedu

Table - 2 Administration and Inspection Schedule

※ 1 Increase from 3 mg to 5 mg of donepezil hydrochloride . The week before the allowable range.

※ 2 Allow 2 weeks before and after .

※ 3 It is implemented in the reinforcement guidance group by "informed consent file" . (Attachment 2)

* 4 Detailed confirmation of the reason for termination is carried out . If you do not visit the hospital, doctor in charge of clinical research, CRC · pharmacist etc investigate until the reason is clarified by telephone etc.

※ 5 It is carried out in advanced Alzheimer's type dementia. From donepezil hydrochloride 5 mg to 10 mg
Is increased.

* 6 When implementation is possible, at the start of administration and at 12 weeks. Furthermore, it is also carried out to the extent possible, at 24 week, 48 week, when stopping, and when increasing from 5 mg to 10 mg of donepezil hydrochloride .

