7.2.2. View

When administered after 2 weeks, when 12 weeks, at week 24, at 48 weeks or when stopped, and examined the following items during increase from donepezil hydrochloride 5 mg to 10 mg, to fill in the case report form.

1) Medication compliance

The doctor in charge listens to subject compliance and evaluates in the following five stages.

① medication 90 % or more ② medication 70 % or more and less than 90 % ③ medication 30 % or more and less than 70 %

④ medication 10 % or more and less than 30 % ⑤ medication taking less than 10 %

2) Cognitive function test

Examine the total score and each item score of MMSE- J . If practicable, perform at the beginning of administration and at 12 weeks. Furthermore, it is also carried out to the extent possible, at 24 week, 48 week, when stopping, and when increasing from 5 mg to 10 mg of donepezil hydrochloride .

3) Adverse event

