9.2 See record of adverse events

Four) Use of concomitant medication

Investigate the drug name. For memantine, we investigate dose and dosing period.

8. End of research , suspension and suspension

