9.2. Record of adverse events

Clinical research physician is, this clinical study for a new adverse events occurring after the start, the event name , serious category (serious, non-serious), severity (mild, moderate, severe) , the expression date, treatment , outcome date (or outcome date confirmed) , outcome (recovery, there has been recovery sequelae, light, non-recovery, death, unknown) and this clinical study causal relationship between (no relation, related Oh might Rukamo , probably related Yes) In the case report.

For abnormal variations in clinical laboratory values judged clinically important by a doctor in charge of clinical research , fill out the case report along with the basis.

Regarding the causal relationship between adverse events and this clinical study , fill in the case report the basis of the judgment.

(1) Causality relationship with this clinical study

1) No relation:

There is no reasonable causal relation between this drug administration and adverse event. (There is no temporal rationality between this drug administration and adverse events, or it is thought that the factors of patients, such as concomitant drugs and original diseases and complications, are greatly influenced by patients.)

2) There may be relevance :

There is a possibility of a reasonable causal relationship between this drug administration and an adverse event. (There is temporal rationality between this drug administration and the adverse event expression and the possibility of a causal relationship with this drug is considered even when considering factors of patients such as concomitant drugs and original diseases and complications Conceivable.)

3) Probably related :

There is a high possibility of a reasonable causal relationship between this drug administration and an adverse event. (There is temporal rationality between this drug administration and the adverse event expression and the possibility of a causal relationship with this drug is

considered even when considering factors of patients such as concomitant drugs and original diseases and complications A similar adverse event is admitted by re - administration.

(2) Severity of Adverse Events

- 1) Mild: degree of discomfort, but not affecting normal daily activities
- 2) Moderate: degree of disruption to normal daily activities due to discomfort
- 3) High level : incapacity or enough to normal daily activities becomes impossible, it was deprived of the activity capacity state

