11.4. Analysis of safety

Subjects who are included in this clinical study and whose test drugs have been administered at least once are subject to safety analysis.

All adverse events are indicated and serious adverse events are separately counted. Drugs agents adverse events observed after administration administration group by type of adverse events for each, categorical adverse events was calculated expression rate, a comparison between groups (adverse events by type, categorical statistical analysis Performed by the data center prior to) .

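### Only the enhanced arm has a prescribed, repeated side-effect explanation at the visits where adverse events and compliance are collected, with no common question or order, so the between-arm adverse event comparison may reflect reporting as well as harm

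*Combined protocol and SAP*

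**What the plan says.** - **Content of the session.** In section 5.2 the enhanced arm uses the file to explain "the pathology of AD, the significance of drug therapy with Aricept®, side effects, etc. to the subject himself and family or caregiver". The third note to Table 2 limits this to one arm: "It is implemented in the reinforcement guidance group by" the file.
- **Timing of the session.** Table 2 marks it at the start of administration, at weeks 2, 12 and 24, and at the 5 to 10 mg increase. Section 5.2 lists week 2 and then "12 weeks, 24 weeks, 48 weeks, and the increase at the time" of that dose step. Section 5.2 therefore includes week 48, which Table 2 leaves blank, and does not list the start of administration, which Table 2 marks.
- **Timing of adverse event and compliance collection.** Section 7.2.2, both arms: "When administered after 2 weeks, when 12 weeks, at week 24, at 48 weeks or when stopped, and examined the following items". The 5 to 10 mg increase is included as well.
- **Method of collection.** For compliance: "The doctor in charge listens to subject compliance and evaluates in the following five stages". For adverse events, section 7.2.2 only points to section 9.2 ("See record of adverse events"). Section 9.2 opens "Clinical research physician is, this clinical study for a new adverse events occurring after the start, the event name" and goes on to list the other fields to be recorded, such as seriousness, severity, dates, outcome and causality.
- **Analysis.** Section 11.4 says that for adverse events by type and category there "was calculated expression rate, a comparison between groups". Section 11.2 sets a two-sided 0.05 level for the tests that follow it. Serious events are counted separately.

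**The concern.** Both arms take the same drug, and the randomised difference is the instruction. Part of that instruction teaches patients and caregivers what side effects are, and a planned outcome is what those same people then report. If the session makes them more likely to notice or mention an event, the enhanced arm shows a higher rate with no extra harm. If the session reassures them, the rate falls. A reader of the final report could take the first pattern as a cost of the instruction or the second as a benefit.

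Compliance has the same exposure. It rests on the patient's account to the doctor, at visits where one arm is also told why the drug matters. Average compliance is a factor in the secondary logistic regression, and section 11.3 compares the influence of factors between groups.

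**Working it through.** **Step 1: overlap of session and collection.** From Table 2 and section 5.2:

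| Visit | File session, enhanced arm | Adverse events and compliance, both arms |
|---|---|---|
| Start of administration | Table 2 yes; section 5.2 does not list it | no |
| Week 2 | yes | yes |
| Week 12 | yes | yes |
| Week 24 | yes | yes |
| 5 to 10 mg increase | yes | yes |
| Week 48 | section 5.2 yes; Table 2 blank | yes |

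The overlap is certain at four visits and unresolved at week 48. Sections 7.2.2 and 9.2 give no question, checklist, order relative to the session, or blinded assessor.

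**Step 2: the plan's own figure.** The plan has no figure for adverse events. Its sample size for continuation (section 12) does reproduce. For 0.49 against 0.73, two-sided 0.05, power 0.8, pooled variance and mean rate 0.61:

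n = [1.96·√(2·0.61·0.39) + 0.8416·√(0.49·0.51 + 0.73·0.27)]² / 0.24² = (1.352 + 0.563)² / 0.0576 ≈ 63.7, so 64 per group, as stated.

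This does not bear on the present point, but the same form of test is used below.

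**Step 3: size of a pure reporting difference.** The assumptions, none of them from the documents, are:
- equal true risk π in both arms;
- the share of events captured is c₀ (control) and c₁ (enhanced);
- n = 75 per arm. The plan gives 150 in total and no allocation ratio.

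Formulas:
- Observed rates: p₀ = π·c₀ and p₁ = π·c₁. False difference: d = p₁ − p₀.
- With p̄ = (p₀ + p₁)/2: se₀ = √(2·p̄(1 − p̄)/75) and se₁ = √(p₀(1 − p₀)/75 + p₁(1 − p₁)/75).
- Chance of a significant result = Φ((d − 1.96·se₀)/se₁) + Φ((−d − 1.96·se₀)/se₁).

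Worked case, π = 0.50, 60% against 95%: p₀ = 0.30, p₁ = 0.475, d = 0.175, se₀ = 0.0796, se₁ = 0.0783. Then (0.175 − 0.1560)/0.0783 = 0.24 and Φ ≈ 0.60. The second term is negligible.

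| π | c₀ | c₁ | p₀ | p₁ | d (points) | Chance of p < 0.05 |
|---|---|---|---|---|---|---|
| 0.20 | 60% | 70% | 0.120 | 0.140 | 2 | 6.5% |
| 0.50 | 60% | 70% | 0.300 | 0.350 | 5 | 10.0% |
| 0.30 | 70% | 85% | 0.210 | 0.255 | 4.5 | 10% |
| 0.50 | 60% | 90% | 0.300 | 0.450 | 15 | 47.5% |
| 0.50 | 60% | 95% | 0.300 | 0.475 | 17.5 | 60% |

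With equal capture, d is 0 and the chance is the nominal 5%.

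**Step 4: single event types.** Section 11.4 also compares by type, where risks are lower. With π = 0.05–0.10 and 60% against 90%, d is 1.5–3 points and the chance about 8–11%.

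**Step 5: masking.** True risks of 0.40 (normal guidance) and 0.30 (enhanced), captured at 60% and 80%, give 0.40 × 0.60 = 0.24 and 0.30 × 0.80 = 0.24. A real 10-point difference disappears.

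**The case against.** **What a reader might infer but the documents do not show.**
- *That only the enhanced arm hears about side effects.* The content of normal guidance is not described, so it may cover them. The consent document must also set out possible risks, for both arms (section 13.2). What differs by design is the prescribed, repeated, file-based explanation.
- *That the same staff teach and then ask.* Sections 7.2.2 and 9.2 name the doctor for compliance and adverse event recording. No section says who delivers the session.
- *That compliance answers are inflated in the enhanced arm.* They may be. Compliance is a five-band rating used as a factor in a secondary analysis, and no direct between-arm test of it is planned.

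**The case against acting.** Adverse events are a secondary item; the key endpoints are continuation and reasons for stopping. Some difference in reporting is inherent in an open education trial and can be handled as a caveat. The attachments and the case report form are not in the documents and may contain standard questions. Every figure in Step 3 is assumed, and for single event types the effect is modest. On Table 2's schedule the enhanced arm has already had one session before the first adverse event visit, so asking before that day's session cannot remove all priming.

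**What stands.** These points limit the importance of the concern and the power of the remedy. They do not supply a common question or an order, and the comparison is still planned without a statement that it is sensitive to reporting.

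**Conclusion.** The point holds as a minor one. The prescribed side-effect explanation goes to one arm, at visits where adverse events and compliance are also collected, and the protocol text does not standardise the enquiry. The comparison in section 11.4 may therefore reflect reporting as well as harm, in either direction.

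The size cannot be derived from the documents. Under equal true risk and an assumed 75 per arm, it runs from 2–5 points and about 6.5–10% rejection (60% against 70% capture, risk 20–50%) to 4.5–17.5 points and about 10–60% (60–70% against 85–95%, risk 30–50%), against a nominal 5%. These are figures for any adverse event. They show what differential capture could do, and do not predict what it will do here. The primary continuation comparison lies outside this point.

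**What to change.** - **Section 7.2.2:** state that in both arms adverse events and compliance are recorded with the same fixed questions before any instruction at that visit.
- **Section 11.4:** state that between-arm differences in non-serious events are descriptive and sensitive to reporting. Show serious events, which are already counted separately, alongside as less open to prompting. Making serious and severe events the main comparison would be a matter of preference and is not needed.
- **Section 5.2 and Table 2:** reconcile the session schedule (week 48 and the start of administration).
- **Section 5.2:** say what normal guidance contains, so that a reader can judge how far the arms differ on side-effect information.

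The cost is a few lines of text, a short question list and a few minutes per visit. The ordering rule removes same-visit priming only. On Table 2's schedule, the session at the start of administration and all earlier sessions carry over to every adverse event visit, which is why the label in section 11.4 is needed as well.
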